- Check and review of the regulatory binder and all essential documents
- Review of all SAEs and subject withdrawals
- Enrollment issues and targets
- Protocol amendments and their approval by the IRB
- Protocol deviations
- Personnel changes and required training
- Verifying continuous institutional review board (IRB) approval
- Any other issue as deemed important to the conduct of the study

Reporting and Follow-up:

If there are any significant findings, the S-I will follow-up any noncompliance, potential noncompliance, data irregularities, or other deficiencies identified along with a description of any actions taken, to be taken, or recommended, including the person responsible for completing actions and the anticipated date of completion.

4.0 Description of the Investigational Device:

Prototype Description:

The cryo-anesthesia device is a handheld instrument measuring approximately 10 inches in length and 1.5 inches in diameter, and weighing 0.8 pounds. A $4 \times 4 \text{ mm}^2$ area at the tip of the device is placed against the eye and cooled to a user-specified temperature setpoint between -5 and -10°C via activation of a switch on the device (**Figure 2**). The temperature setpoint is selected prior to device activation. Ocular surface cooling slows conduction of pain fibers in the conjunctiva (outermost layer of the eye) and the sclera (white of the eye) to a depth less than a millimeter. The key features of the device include a temperature regulating feedback loop that maintains highly accurate and precise temperature control and an integrated timer that controls the duration of cooling, both of which facilitate sufficient cooling and prohibit excessive cooling. Two small protrusions on the tip leave temporary indentations on the surface of the eye to guide placement of the intravitreal needle. The cooling region of the device is located on a replaceable metal tip. An “ON” switch is first activated to cool the contact region of the device, after which this region is placed against the eye, initiating rapid cooling to anesthetize the injection site while simultaneously marking the cooled location. After the specified cooling time is reached, the device is removed, immediately after which the physician performs intravitreal injection.

Figure 2 | Cryoanesthesia device.

Safety Features:

- At maximum power, the device achieves a temperature of -12°C. Any device malfunction would result in an increase in this temperature rather than a decrease.
- Prior studies as well as our own histological studies with rabbits indicate that this minimum cooling temperature (-12°C) is not low enough to cause ocular tissue damage, even with extended exposure. For the purpose of the study, the device will not be set to a temperature colder than -10°C.
- A temperature regulating feedback loop maintains highly accurate and precise temperature control, and an integrated timer controls cooling time.
- The device tip is replaced with a new sanitized or sterile tip before each use to help ensure safe contact with the eye surface.
- Device tip indents the eye surface, guiding subsequent needle placement.
- Ergonomic and lightweight design, facilitating safe use on or near the eye.
- Low operating voltage (11 V).

Prototype Description:

The device uses thermoelectric (Peltier) cooling to create the low temperature required for cryoanesthesia; thermoelectric cooling has the advantages of being lightweight, small, solid-state (thus no fluids or moving parts), and electrically driven (thus allowing straightforward control of temperature). The device uses a unique design for efficient heat spreading in which an inner arm made from a thermally conductive metal (1 in Fig. 3: cold arm) is simultaneously cooled by a group of Peltier modules (2 in Fig. 3) and is thus able to achieve a large cooling power and maintain a low temperature at the cooling surface on the replaceable tip (3 in Fig. 3). This configuration also allows the Peltier modules to reject heat to an area of a heat sink (4 in Fig. 3) that is not only large and hence efficient but also extended away from the cooling surface, thus allowing a narrow shape with better visual clearance during use.

[figure not shown]

Figure 3 | Device structure. 1—cold arm, 2—Peltier module, 3—replaceable cold tip, 4—heat sink, 5—air inlet, 6—air vent, 7—vice-like mechanism, 8—protrusions

Air is received from the inlet openings (5 in Fig. 3) by an electric fan, cools the fins, and exits through vents at a location far from the replaceable tip (6 in Fig. 3). The location of the vents far from the replaceable tip not only reduces parasitic convection heating at the tip surface but also prevents the airflow from drying the eye surface. A rechargeable lithium ion battery pack (28 Wh), which provides sufficient energy on a single charge to operate the device at -10°C for approximately one hour (~100 treatments), can be easily removed from the rest of the device to facilitate simple charging.

Temperature control is achieved by an electrical feedback loop that samples the tip temperature using a thermal sensor and provides appropriate power to the thermoelectric coolers via pulse width modulation (PWM) of the DC battery source. While the cooling surface is unable to reach a temperature lower than -12°C when the device is operated at typical room temperature (20°C), a failsafe automatically powers the device off if the cooling surface falls below -12°C. Other automatic power offs occur if the battery temperature exceeds 60°C or the heat sink temperature exceeds 50 °C. A single button on the device is used to set the cold tip temperature and timer duration, as well as power the Peltier modules. Operation of the button comprises: 1) Clockwise rotation to increase the cold tip temperature setpoint, 2) Counter-clockwise rotation to decrease the cold tip temperature setpoint, 3) Clockwise rotation while the button is pushed, to increase the timer duration, 4) Counter-clockwise rotation while the button is pushed, to decrease the timer duration, and 5) Double-pressing to activate the Peltier modules. A second tactile button located near the grip position is used to activate (or deactivate) the timer. When the timer is activated, the device produces two consecutive beeping sounds at low and high frequencies, followed by beeping sounds every 10 seconds during the timer duration, and finally two long consecutive beeping sounds at high and low frequencies when the timer

duration has expired. If the “Timer” button is pushed again before the set time is reached, two short consecutive beeps at high and low frequencies occur and the timer is immediately terminated.

A user readies the device by first inserting the replaceable tip into the cold arm. A vice-like mechanism (7 in Fig. 3) is used to provide both convenient tip replacement and sufficient pressure between the replaceable tip and cold arm for good thermal contact. The replaceable tip is coated by a thin hydrophobic polymer layer that mitigates ice adhesion between the device and tissue. Two small protrusions (8 in Fig. 3) on the replaceable tip leave temporary indentations on the eye surface to guide subsequent treatment (e.g., placement of the intravitreal injection needle 3 or 4mm from the corneal limbus).

After setting the desired cold tip temperature setpoint and timer duration and inserting the replaceable tip, the user operates the device by first double-pressing the main (“rotation & push”) button, which turns on the Peltier modules and brings the tip temperature to the setpoint (this takes approximately 20 seconds for a setpoint of -10°C). He or she then brings the tip into contact with the patient’s eye and presses the “timer” button (which responds with a beep). If the timer duration is set to 10 (or 30) seconds, the device maintains -10 °C for 10 (or 30) seconds and then beeps. After the timer duration, the device returns to ambient temperature.

There are no anticipated changes to the device during the course of this study.

5.0 Future Studies:

We plan to conduct a second phase of the study where we will compare the SOC to only one cryoanesthesia temperature setpoint and one time setpoint, selected after the analysis of the first 40 patients.

References:

Beckman, H., S. Leff and H. S. Sugar (1975). "Scleral bursting strength. Results after treatment with ruby laser, cryotherapy, or diathermy." *Arch Ophthalmol* **93**(6): 428.

Blaha, G. R., E. P. Tilton, F. C. Barouch and J. L. Marx (2011). "Randomized trial of anesthetic methods for intravitreal injections." *Retina* **31**(3): 535-539.

Chi, H. H. and C. D. Kelman (1967). "Histopathology of corneal endothelium after freezing." *Int Ophthalmol Clin* **7**(2): 369-380.

Curtin, V. T., T. Fujino and E. W. Norton (1966). "Comparative histopathology of cryosurgery and photocoagulation. Observations on the advantages of cryosurgery in retinal detachment operations." *Arch Ophthalmol* **75**(5): 674-682.

Davis, M. J., J. S. Pollack and S. Shott (2012). "Comparison of topical anesthetics for intravitreal injections : a randomized clinical trial." *Retina* **32**(4): 701-705.

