Patients receiving SOC undergo the risk of increased corneal keratopathy. In addition, patients receiving the SOC have an increased risk of post injection pain. The risk of mild ocular discomfort

with CA is mitigated by the use of proparacaine and also poses less risk to patients than topical lidocaine.

1.3.1 Primary Objective:

We plan to carry out a pilot study to collect preliminary data on the effectiveness of the cryoanesthesia (CA) device in minimizing the pain caused by intravitreal injections (IVT) and determine the most effective temperature and time of treatment. Specifically, we intend to record patients' subjective injection pain. The study will be carried out in patients receiving bilateral injections, and one eye will be anesthetized using the CA device, with the fellow eye receiving anesthesia via a topical lidocaine gel (SOC), a common method of providing anesthesia in current clinical practice.

1.3.2 Exploratory Objective(s):

We will measure injection preparation pain, 4-hr, and 24-hr post injection pain. Patients will rate ocular irritation immediately after injection as well as 4 and 24 hours after injection (1 – no irritation; 2 – mild irritation 3 – moderate irritation 4- marked irritation). Patients will rate visual function in the treated eye immediately after injection as well as 4 and 24 hours after injection (1 – no changes from baseline; 2 – mild blurring of vision 3 – moderate blurring of vision 4- marked blurring of vision). Physicians will record patients' objective response to intraocular needle penetration (1 – no pain/movement; 2 – mild pain/movement 3 – marked pain/movement with the injection). In addition, physicians will record the following common ocular side effects following IVT: subconjunctival hemorrhage (SCH), conjunctival hyperemia, and conjunctival injection. These will be assessed via a slit lamp examination performed within 30 minutes and 24 hours of the administration of the intravitreal injection. In addition, each eye will be assessed for other signs of anterior segment toxicity, including AC reaction or hypotony. Patients will be examined or receive a call 1 week after the injection to assess any adverse effects.

1.4 Anticipated duration of the clinical investigation:

[figure not shown]

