We plan to recruit 40 patients for this study, and each patient will receive a single injection in each eye. Most patients receiving bilateral injections receive both injections in a 1-2 week period (1 eye at day 0, and the second eye by day 14). This is the current standard period between intravitreal injections, and is used regardless of the form of local anesthesia delivered. Some patients receive bilateral injections during the same clinic visit. First eye treatment will be randomly assigned to one of the CA treatment groups and the other eye will be randomly assigned to SOC.

2.0 Study Design:

2.1 General Study Design:

Prospective, interventional pilot study.

2.1.1 Study Design Schematic:

2.2 Subject Selection:

2.2.1 General characteristics of the proposed subject population(s):

Patients age >18 years old with bilateral macular disease due to either exudative macular degeneration or diabetic retinopathy requiring bilateral IVT and who had at least one prior IVT. To be included in this study, patients must be able to give informed consent.

Patients with bilateral macular disease requiring bilateral IVT will enable us to compare the effectiveness of CA compared to SOC in terms of pain reduction, with each patient serving as their own control.

2.2.2 Anticipated Number of Research Subjects:

We anticipate recruiting and enrolling 40 patients to complete this study (10 for each CA group). We expect that all 40 patients will complete the study.

2.2.3 Inclusion Criteria:

Inclusion criteria: Patients age >18 years old with bilateral macular disease due to either exudative macular degeneration or diabetic retinopathy requiring bilateral IVT. Only patients with at least one previous IVT will be recruited. To be included in this study, patients must be able to give informed consent.

2.2.4 Exclusion Criteria:

Exclusion Criteria: Patients < 18 years of age. Patients with unilateral disease, or patients with bilateral disease who are not able to give informed consent. Patients with preexisting conjunctival, episcleral or scleral defects or disease will be excluded.

2.3 Study Procedures:

2.3.1 Screening Procedures:

Physician will verify the need for IVT prior to beginning the study.

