After obtaining written consent, the brow above the eye to receive intravitreal treatment will be marked. Next, one drop of proparacaine will be applied into the eye to at least 5 minutes before any additional steps. Once the patient is ready, another drop of proparacaine will be applied and the physician or his assistant will then swab the lids with betadine. The physician will place a lid speculum in the patient’s eye. A drop of betadine will be applied at the site of treatment. The physician or his assistant will then activate the CA device by pressing the main button. He or she will review the LED display to verify that the device is set to achieve the correct temperature and time setpoints depending on the arm of the study to which the patient is randomized. The physician will adjust the temperature and time set points using the main device button if they are not correctly entered. The physician will then verbally review the selected treatment temperature and time, after which he or she will activate the device to enable the device tip to reach the required temperature. Immediately prior to placing the device tip against the eye, the physician will press the activation switch, after which he or she will apply the device to the surface of the eye. When the timer sounds, he or she will remove the device from the surface of the eye. The device tip has markers on it that will leave a temporary indentation 3 and 4 mm from the limbus. Immediately before giving the injection, the physician will place a drop of betadine on the surface of the eye at the site marked for the injection and wait 20 seconds. The physician will then give the intravitreal injection.

The procedure for the patients receiving SOC will be similar to that described above. After obtaining written consent, the brow above the eye to receive intravitreal

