treatment will be marked. Next, one drop of proparacaine will be applied into the eye to receive at least 5 minutes before any additional steps. Once the patient is ready, another drop of proparacaine will be applied and the physician or his assistant will then swab the lids with betadine. The patient will then have lidocaine gel placed on the eye and left in place for a minimum of 3 minutes prior to IVT. The 3-minute waiting period is needed to allow the lidocaine gel to diffuse through the sclera. Following completion of numbing, the eyelids will be swabbed with betadine and the physician will place the lid speculum. The physician will use a caliper to measure 3 or 4 mm from the limbus of the eye, place a drop of betadine over this spot, wait 20 seconds and then administer the injection.

2.3.2.1 Allocation to Treatment:

Patients will be randomly assigned to 1 of the 4 CA treatment groups and the SOC arm. Patients will be randomized to have their first eye receive either CA or SOC.

2.3.2.2 Treatment Adherence/Study Compliance:

If a patient is does not require, or refuses, an injection in either eye, they will be removed from the study. Because IVT prevents blindness, the refusal of IVT is extremely rare. In addition, it is extremely rare for patient who have been determined to need IVT to have improvement in vision prior to IVT.

If patients withdraw from the study, we will plan to recruit additional patients to replace them.

2.3.3 **Follow-up Procedures:**

2.3.3.1 Procedures to Assess Efficacy:

Patients will record their subjective pain (pre-injection preparation pain, injection pain, and 24 hr post injection pain) using a visual analog scale (1 to 10, with 10 being severe pain and 1 being no pain). The study coordinator will call the patients within 4 hours after their injection to review their 4-hr post procedure pain scores with them. Patients will be asked to return in 24 hours for anterior segment examination and 24-hr post injection pain assessment. Patients treated on Friday will be asked to return on Saturday for their 24-hr post injection assessment.

2.3.3.2 Procedures to Assess Safety:

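### The spoken check of the cryoanesthesia setpoints can tell the patient, who rates the primary endpoint, which temperature was assigned; this is a possible, partial and easily avoided unmasking

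*Protocol*

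**What the plan says.** The injection procedure in Protocol section 2.3.2 fixes the order of steps for the CA eye: proparacaine, lid swab, lid speculum, betadine, then switching on the device, which the physician or an assistant may do. Next comes the display check: "He or she will review the LED display to verify that the device is set to achieve the correct temperature and time setpoints". Then comes any correction: "The physician will adjust the temperature and time set points using the main device button if they are not correctly entered". After that, "The physician will then verbally review the selected treatment temperature and time", and only then is the tip cooled, applied and removed, and the injection given. No listener is named for the spoken review.

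Section 2.3.2.1 states the allocation: "Patients will be randomly assigned to 1 of the 4 CA treatment groups and the SOC arm". Section 2.2.2 gives the group size as "10 for each CA group", 40 patients in all. The primary objective (section 1.3.1) includes to "determine the most effective temperature and time of treatment". Section 2.4.1 makes injection pain, scored from 1 to 10, the primary endpoint, and section 2.3.3.1 makes the patient the rater: "Patients will record their subjective pain". Section 5.0 carries one temperature and one time into a second phase after the first 40 patients are analyzed.

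The protocol makes no statement on masking and does not tell staff to keep the CA setting from the patient.

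**The concern.** The setpoints define the randomized CA group. Saying them aloud beside the patient tells the person who supplies the primary outcome which group they are in, before they rate it. Pain scores are subjective, and a patient who believes that a colder tip numbs better, or hurts more, may rate accordingly.

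What is at stake is the comparison among the four CA settings. Each patient has a single exposure to the device (section 3.1), so settings are compared between patients. Using the patient as their own control does not protect this comparison. The procedure for the standard-of-care (SOC) eye has no spoken setting, so any reaction to the spoken value stays in the CA-minus-SOC difference and is confounded with the setting. A later analysis could not separate the two.

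**Working it through.** The point is procedural, so the main check sets the sections side by side.

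1. **Is the patient present and awake?** The speculum is placed before the device is switched on, so the patient is in place. Sections 1.3 and 2.3.2 describe only topical drops before CA, the patient rates preparation and injection pain, and the physician scores the patient's movement. Awake is an inference, but a firm one.

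2. **Does the spoken review add information?** Duration is largely known anyway: section 4.0 has the device beep every 10 seconds and again when the timer expires. Temperature is different. Cold may be partly felt, since section 1.3 lists mild discomfort from it as a risk, but no other described step gives the patient the numeric temperature. The added information is therefore mainly temperature.

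3. **Does the review serve a purpose?** Yes. The display check may be done by the assistant and comes before any correction. Section 4.0 says "A single button on the device is used to set the cold tip temperature and timer duration", so one control sets both values. The spoken review is the only verification listed after adjustment.

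4. **Can it be done without the patient hearing?** The setpoints are on the LED display, so they can be confirmed by eye.

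5. **Which comparison is exposed?** The stated numbers agree: 4 CA groups × 10 patients = 40. An SOC eye gets gel and a CA eye gets a cold probe, so the described procedures already let a patient tell CA from SOC. The spoken value adds something only to the comparison among CA settings.

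**Scale only.** The protocol gives no SD, no expectation effect and no selection rule, so every input here is assumed: SD 2 points, 10 patients per setting, the lowest observed mean is selected, and one setting is truly 1 point better than three equal ones.

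- Standard error of a group mean = SD/√n = 2/√10 = 0.632.
- Observed means are taken as normal around (−1, −s, 0, 0), where s is a shift in one rival's mean due to expectation alone. The probability that the first mean is lowest, by numerical integration, is 0.724 at s = 0, 0.709 at s = 0.1 and 0.621 at s = 0.5.
- If the 0.5-point shift falls on the truly better setting instead, the probability rises to 0.889.
- If the 0.5-point shift is equally likely to fall on any of the four settings, it is (0.889 + 3 × 0.621)/4 = 0.688, against 0.724 with no shift. That is a fall of 0.036.
- With no shift at all, the better setting is missed with probability 1 − 0.724 = 0.276.

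Under these assumptions, sampling noise at 10 per group outweighs the cue.

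**The case against.** The strongest case against has four parts.

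- **No promise is broken.** The protocol calls itself a prospective interventional pilot and never claims masking. This stands: there is no contradiction. The point is only that a prescribed step discloses the assignment when it need not.
- **The harm depends on what is not shown.** A patient hears one setting and may have nothing to rank it against. The consent wording is not available. If it already discloses the assigned setting, the spoken review adds little. If it says nothing about the other settings, the effect may be zero. This stands and limits the claim.
- **Masking would be incomplete anyway.** Beeps reveal duration, cold may be felt, and the physician knows the setting. This also stands, so the gain is partial.
- **The spoken review is a safety check.** It follows adjustment on a device where one button sets both values, and an assistant may catch an error by ear. This limits the remedy without defeating the point. A real check of the actual setpoints must remain, and a coded label alone should not replace it.

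A reader might infer that the spoken review biases CA against SOC, or that the choice of setting is shown to be biased. The documents support neither. The first comparison is not masked from the patient in any case. For the second, the documents give neither a direction nor a size, and they do not say what patients know about the other settings.

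**Conclusion.** The point holds as a potential, avoidable unmasking of the outcome rater, mainly to temperature, that affects the comparison among the four CA settings. It rests on two inferences: that the patient is awake, and that a review spoken at that stage is within the patient's hearing. Any distortion also requires patients to know or guess how their setting ranks.

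Size and direction cannot be derived from the documents, and the effect may be zero. The selection probabilities above show scale only: all inputs are assumed, and choosing the lowest mean is not a rule the protocol states. This is a low-priority improvement to the procedure, not a demonstrated bias or an error in a figure.

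**What to change.** In the injection procedure of section 2.3.2, keep the physician's confirmation of both actual setpoints, placed after any adjustment and before the device is activated. Specify that it is made visually against the LED display, or out of the patient's hearing. If a second check is wanted, have the assistant read the display as well. Add a sentence that patients are not told their CA temperature until their last 24-hour rating is recorded, whichever eye is treated second.

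The cost is one or two sentences and a small change in staff routine. The spoken read-back is lost, so the visual check must fully replace it. Masking stays partial, and the consent wording, which is not shown, must match.

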2.3.2 Study Treatment or Diagnostic Product Procedures:*Device Overview:*

The cryoanesthesia device is a handheld instrument measuring approximately 10 inches in length and 1.5 inches in diameter. A 4×4 mm area at the tip of the device is placed against the eye and cooled to the temperature setpoint (e.g., -5°C, -7°C, or -10°C) via activation of a switch on the device. Cooling slows conduction of pain fibers in the conjunctiva (outermost layer of the eye) and the sclera (white of the eye) to a depth less than a millimeter. The key features of the device include a temperature regulating feedback loop to maintain highly accurate temperature control and a lockout mechanism to prevent excessive cooling. Two small protrusions on the tip leave temporary indentations on the surface of the eye to guide subsequent placement of the intravitreal needle. The cooling region of the device is located on a replaceable metal tip. An “ON” switch is first activated to cool the contact region of the device, after which this region is placed against the eye, initiating rapid cooling to anesthetize the injection site while simultaneously marking the cooled location. After the specified cooling time is reached, the device is removed, immediately after which the physician performs intravitreal injection.

Instructions for administering CA:

All physicians taking part in this study will receive a practical training session on use of the prototype prior to study initiation to ensure that they are comfortable operating the device.

Injection procedure:

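### Do the differing descriptions of the cryoanesthesia sequence (betadine wait before the needle, moment the timer starts) undermine the comparison?

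*Protocol*

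**What the plan says.** **Removal to needle.** The Device Overview in Section 2.3.2 states: "After the specified cooling time is reached, the device is removed, immediately after which the physician performs intravitreal injection". The first Prototype Description in Section 4.0 repeats that sentence. The Injection procedure in Section 2.3.2 is the step list for the CA eye. After device removal it adds a further step, "the physician will place a drop of betadine on the surface of the eye at the site marked for the injection and wait 20 seconds", and only then the injection. The step list for the SOC eye ends in the same way: "place a drop of betadine over this spot, wait 20 seconds and then administer the injection".

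**Timer start.** In the CA step list, after checking the set points, "he or she will activate the device to enable the device tip to reach the required temperature". Then: "Immediately prior to placing the device tip against the eye, the physician will press the activation switch". The device is applied, and the end of treatment is given as: "When the timer sounds, he or she will remove the device from the surface of the eye". Section 4.0 describes two controls. The main button sets temperature and duration and powers the cooling modules. For the other it says: "A second tactile button located near the grip position is used to activate (or deactivate) the timer". The operating description that follows in Section 4.0 has the tip brought to the eye first and the timer button pressed next.

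**A side point.** Section 1.3 (Risk Analysis) gives the coldest planned temperature as -10°C and puts 23°F beside it.

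**The concern.** The pilot is meant to identify the best temperature and duration of cooling for injection pain (Section 1.3.1), with 10 patients per CA group (Section 2.2.2). One temperature and one duration then go forward (Section 5.0). Exposure lasts 10 to 20 s (Section 3.1), so a 20 s gap before the needle is as long as the cooling itself, or twice as long. If some operators waited and others did not, the numbing could have faded to different degrees when the needle went in.

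The timer raises a similar worry. A press before contact makes actual contact shorter than the set time, and a press after contact makes it at least the set time. Since duration is one of the factors under study, mixed practice would blur the quantity being selected and add noise to small groups. The 20 s also lies inside the procedure-time endpoint in Section 2.4.1.

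**Working it through.** The protocol states no figure for either interval, so this is mainly a comparison of texts with some small arithmetic.

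**1. Are there two rival instructions on removal to needle?**
- The overview sentence gives no step between removal and needle; the CA step list gives a drop and a wait of 20 s.
- The overview also leaves out the proparacaine drops, the lid swab, the speculum, the first betadine drop and the check of the set points. Its silence on the second betadine drop is therefore of the same kind as its other silences.
- The CA step list itself describes the drop and wait as done immediately before the injection. The protocol's own use of that adverb thus accommodates the step.
- Both step lists, CA and SOC, contain the drop and the wait. No step list omits them.

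**2. Size relative to exposure.** 20/20 = 1 and 20/10 = 2, so the wait is 1 to 2 times the cooling time. If every CA eye follows one sequence, this gap is common to all CA groups.

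**3. Size relative to the procedure-time endpoint.** Section 2.4.1 (exploratory endpoint 7) times from proparacaine instillation to injection but does not say from which of the two drops. The SOC list has at least 5 minutes after the first drop, gel "left in place for a minimum of 3 minutes prior to IVT", and the 20 s wait.
- From the first drop: 300 + 180 + 20 = 500 s at least; 20/500 = 4%.
- From the second drop: 180 + 20 = 200 s at least; 20/200 = 10%.
- When both step lists are followed, each eye contains the same 20 s, so it cancels in the within-patient difference.

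**4. Which control is the switch pressed before contact?** By that point the CA list has already started cooling, and Section 4.0 gives only two controls, so by elimination it is probably the timer button. The CA list does not say so. If it is some other control, the list simply leaves out the timer press, and Section 4.0 supplies it.

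**5. Effect of the timer order.** The documents give no placement lag. Assume L = 1 to 3 s, for illustration only.
- Press before contact: contact = set time − L. At 10 s this is 9 to 7 s (10% to 30% short); at 20 s it is 19 to 17 s (5% to 15% short).
- Difference between the two settings under one rule: (20 − L) − (10 − L) = 10 s, whatever L is.
- Mixed practice at the extreme: a 20 s setting pressed 3 s early gives 17 s of contact, and a 10 s setting pressed 3 s late gives 13 s. The settings move closer but keep their order.

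**6. Temperature conversion.** F = C × 9/5 + 32. For -10°C: -18 + 32 = 14°F. For -5°C: -9 + 32 = 23°F. The Fahrenheit figure does not match the Celsius one. The device set points in Sections 2.3.2 and 4.0 are all in °C, so no treatment step uses the Fahrenheit value.

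**The case for a change.** The strongest case for a change is that the literal texts cannot both hold. The overview stands in the same section as the step list, its sentence appears twice, and nothing says which text governs. The timer order matters more than it may seem: Section 4.0 says the device returns to ambient temperature once the set time has run, so seconds lost before contact are not recovered. Training can standardise practice only if the text being taught is consistent.

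Part of this stands. The timer-start wording is ambiguous, and the CA step list would be clearer if it named the button. The overview sentence is loosely written, and the Fahrenheit figure is a slip.

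What does not stand is the step from loose wording to a damaged comparison. The harm requires operators to differ in practice, and the documents give no sign of that. Section 3.2 describes a single site, and Section 2.3.2 has every participating physician trained on the device before the study starts. The operating text in Section 4.0 is general device description: its example durations are 10 and 30 s, while study exposure is 10 to 20 s. No effect on pain can be computed from the documents.

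**Conclusion.** No change to the plan is called for. On removal to needle, the apparent conflict is a summary sentence set against a step list, and the step lists agree across the two eyes. On the timer, there is a genuine but small ambiguity of unknown size. Under an assumed lag of 1 to 3 s it would shorten contact by 5% to 30%, while leaving the 10 s spacing between 10 s and 20 s settings intact under any single rule. The 20 s wait is 4% or 10% of the minimum SOC procedure time and drops out of the between-eye difference when both lists are followed.

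This rests on two assumptions: operators at the one site work to one taught sequence, and the step lists are what they work from. The design, sample size, endpoint definitions and group comparisons are unaffected. The timer wording, the overview sentence and the °C/°F pair should be reconciled as ordinary editing whenever the text is next revised. No view is taken here on which sequence, duration or temperature is right.
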